16.2. Stata code

Table 16.2 provides sample Stata code for the analysis, each outcome (see section 6.2) will be analysed the same therefore the code below will be used for all outcomes.

Outcome	Stata code
SIMS	<pre>mixed sims sims_b i.letstalk##i.TimePoint CentreNo: deleverymode: StudyNo: c sims sq is continuous sims _b is continuous baseline score letstalk binary (coded 0 for TAU and 1 Let's Talk plus TAU TimePoint is a categorical variable corresponds to the follow-up time points (coded 2 = 2.5 months, 6 = 6 months) CentreNo categorical (corresponds to each recruiting centre) deleverymode 0 = in person; 1 = remote StudyNo is a unique participant identifier Treatment effect for 2.5 months lincomest _b[1. letstalk] Treatment effect for 6 months lincomest _b[1. letstalk] + _b[1. letstalk #6.TimePoint]</pre>

Table 16.2 Stata code

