6.3. Mediators

We will collect data on the below potential mediators of change to determine feasibility of collecting these measures in a definitive trial to answer important hypotheses about mediators:

- 1. Internalised Shame Scale (ISS)¹⁵;
- 2. Self-Esteem Rating Scale (SERS)¹⁶.

7. Timing of Outcome Measurements

Outcome Measure	Baseline	End of treatment (2.5	6 months ¹
		months ¹)	
SIMS	~	√	√
DDS	~	\checkmark	\checkmark
Stigma Stress Scale	~	\checkmark	\checkmark
QPR	~	\checkmark	\checkmark
CDS	✓	\checkmark	\checkmark
SIAS	✓	\checkmark	\checkmark
MANSA	✓	\checkmark	\checkmark
RES	~	\checkmark	\checkmark
Economic patient	✓	\checkmark	\checkmark
questionnaire			
EQ5D-5L	✓	✓	\checkmark
ISS	✓	✓	\checkmark
SERS	\checkmark	\checkmark	\checkmark

¹ post-randomisation

8. Progression criteria

The progression criteria to a definitive trial are:

- Recruitment rate within ≥80% (green); 79-60% (amber); <60% (red) of planned target.
- Retention of participants within the study with ≥ 80% (green); 79-60% (amber);
 <60% (red) of data for the Semi-structured Interview Measure of Stigma (SIMS⁶)

or Stigma Stress Scale⁷, which are the proposed primary outcomes for a definitive trial.

 ≥ 80% (green); 79-60% (amber); <60% (red) of those allocated to Let's Talk receiving at least two sessions.

9. Adverse Events

A serious adverse event (SAE) is:

- All death;
- Suicide attempts;
- Serious violent incidents;
- Any other life-threatening incident;
- Admissions to a psychiatric hospital;
- Formal complaints about the study.

Please see the Study Protocol for more details on AEs. The number SAEs and the proportion of participants with an event will be presented. These will be tabulated and not analysed and will be summarised by Intention-to-Treat (ITT) and as treated.

10. Sample Size and Power Calculation

Outcome data on 60 participants is needed to estimate the standard deviation (SD) required for a sample size calculation for a definitive trial. We have used the advice from Whitehead et al¹⁷ to plan ahead for a trial with 90% power and potential small-to-moderate effect size (standardised effect size ranging from 0.2 to 0.4). To allow 20% attrition, we will recruit 75 participants. A pilot study of this size will allow to test procedures and gather information on other trial design and process elements that are listed in the objectives section.

11. Statistical Methods

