11.1. General Methods

All the main analyses will be based on the ITT principle. Final analysis will take place after full recruitment and follow-up. The results of the trial will be presented following the Consolidated Standards of Reporting Trials (CONSORT) 2010 Statement: extension to randomised pilot and feasibility trials¹⁸. As this is a feasibility trial, the main focus will be to summarise baseline and follow-up data using the appropriate descriptive statistics and graphical summaries. However, we will also look at treatment effects which will be presented with 95% confidence intervals (CIs). There will be no adjustment to secondary outcomes for multiple testing. All eligible participants will be included in the analysis and who provided consent. Any post-randomisation exclusions will be removed and reported as such and agreed with the PMG. Model assumptions will be checked and dealt with appropriately. See Appendix (section 16) for how patient reported outcome measures (PROMS) are derived along with Stata code for the analysis of the outcomes.

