11.4. Outcome measures

To inform a definitive trial analysis, the proposed outcomes (see section 6.2, apart from economic patient questionnaire) will be analysed using repeated-measures mixed-effects regression model correcting for baseline score and time as a categorical fixed effect and centre, mode of delivery, and participant as a random effect. The repeated measures will be assessed at 2.5 and 6 months post-randomisation with treatment effects estimates from a time-by-treatment interactions at each time point. Data missing at baseline will be reported as such. For the analysis, missing baseline data will be imputed using the centre-specific mean of that variable. Economic data collected by the economic patient questionnaire will be summarised using appropriate descriptive statistics.

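### Neither Section 11.4 nor the printed Stata code fixes REML or a small-sample degrees-of-freedom method; on Stata's defaults the 95% intervals would be about 4 to 5% too narrow at 60 participants (minor)

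*SAP*

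**What the plan says.** Section 11.4 specifies a "repeated-measures mixed-effects regression model correcting for baseline score and time as a categorical fixed effect", with centre, delivery mode and participant as random effects. It adds that "The repeated measures will be assessed at 2.5 and 6 months post-randomisation", with one treatment effect estimated at each time. It does not say whether the model is fitted by ML or restricted maximum likelihood (REML), or which reference distribution the intervals use.

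Section 16.2 is the only other place where this could be settled. It opens with "Table 16.2 provides sample Stata code for the analysis" and says that "the code below will be used for all outcomes". The fixed part reads "mixed sims sims_b i.letstalk##i.TimePoint" and the random part "CentreNo: deleverymode: StudyNo: c". No estimator or degrees-of-freedom option is visible. The two `lincomest` lines that form the treatment effects carry no small-sample option.

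On reporting, Section 11.1 states that "we will also look at treatment effects which will be presented with 95% confidence intervals (CIs", and Table 13.4 has columns for the mean difference, 95% CI and p-value. On size, Section 10 says "Outcome data on 60 participants is needed to estimate the standard deviation (SD" for the definitive trial, and plans to recruit 75 to allow for 20% attrition.

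**The concern.** ML estimates variances as if the fixed effects were known, so it understates them by a factor that matters in small samples. Normal quantiles then ignore the fact that the variance was itself estimated. Both errors shorten the interval and lower the p-value.

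Section 6.2 lists ten outcomes and Section 11.4 excludes only the economic questionnaire from modelling. That leaves 9 outcomes at 2 time points, or 18 intervals labelled 95%, all from the same code. Section 11.4 also says the modelling is meant to inform the definitive trial's analysis, so a weakness in this template could be carried forward.

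**Working it through.** **Inputs.**
- Participants with outcome data: 60; recruited: 75; attrition: 20% (Section 10).
- Lower case: 45, which is 60% of 75, the amber/red retention boundary in Section 8.
- Two follow-ups; fixed terms baseline, arm, time and arm-by-time; centre, mode and participant random (Section 11.4, Table 16.2).
- Correlation between the two follow-up scores given baseline: not in the SAP. **Assumption:** 0.3 to 0.7.
- ML with normal quantiles as the default of `mixed`: a property of the software, not stated in the SAP.

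**The plan's own figure.** 60 / (1 − 0.20) = 75. This reproduces.

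**Counting parameters.** Three fixed parameters act between persons: intercept, baseline and arm. Time and arm-by-time act within persons. Centre and mode are in the random part and do not add to the three.

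**Closed form at participant level.**
- Variance ratio, ML to REML: (n − 3)/n
- Standard error ratio: √[(n − 3)/n]
- Width ratio, ML with z to REML with t: 1.960 × √[(n − 3)/n] / t(0.975, n − 3)
- Coverage of ML with z: P(|t on n − 3 df| < 1.960 × √[(n − 3)/n])

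For n = 60: 57/60 = 0.950; √0.950 = 0.975; t(57) = 2.002; 1.960 × 0.975 / 2.002 = 0.954; coverage 93.9%.

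| n | Variance ratio | SE ratio | t | Width ratio | Coverage |
|---|---|---|---|---|---|
| 45 | 0.933 | 0.966 | 2.018 | 0.938 | 93.5% |
| 60 | 0.950 | 0.975 | 2.002 | 0.954 | 93.9% |
| 75 | 0.960 | 0.980 | 1.994 | 0.963 | 94.1% |

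**Simulation with a random participant intercept and two follow-ups** (20,000 runs per setting, n = 60, correlation 0.3, 0.5 and 0.7; true variance 1).
- ML with z: coverage 94.0 to 94.5%, mean variance 0.953 to 0.955.
- REML with t on 57 df: coverage 95.1 to 95.6%, mean variance 0.998 to 1.001.
- Width ratio: 0.955 to 0.957.

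The same simulation gives a width ratio of 0.941 to 0.943 and ML coverage of 93.6 to 94.1% at n = 46. At n = 74 it gives 0.964 to 0.965 and 94.1 to 94.5%.

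**Simulation with the nested structure** (2 centres, 2 modes within each, participant; n = 60; 700 runs for each of two variance settings).
- Width ratio 0.958 to 0.960.
- ML variance 0.948 to 0.953.
- ML coverage 93.0 to 94.0%.

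The Monte Carlo error on coverage is √(0.94 × 0.06 / 700), about 0.9 points. This run therefore confirms the width and variance ratios, but is too small to separate the methods on coverage: REML with t gave 93.7 to 95.7%.

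**The case against.** **The code line is damaged.** The level separators are missing and the line ends in a stray letter, which is where Stata options would stand. Section 16.2 also calls the code a sample. A reader might infer that the SAP chose ML. The documents do not support that. They show only that neither the prose nor the visible code fixes the estimator or the degrees of freedom. This objection stands, and it limits the claim. It does not remove the gap in Section 11.4, and the `lincomest` lines are legible and carry no small-sample option.

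**Larger effects do not fit this model.** Counting five between-person fixed parameters would give 55/60 = 0.917, a variance about 8% low, and coverage of 93.4%. That treats centre and mode as fixed, whereas Section 11.4 and the code make them random. The three-parameter figures apply.

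**The definitive trial's sample size.** A reader might infer that it will come out too small. For a fixed difference in score points, sample size is proportional to the variance, so it would be about 5% low if the SD were taken from the ML fit. The SAP never says it will be. Table 13.4 plans ordinary SDs by arm and time point, which do not carry this bias. Nor is supplying a variance the trial's main purpose: Section 2 gives that as feasibility and acceptability.

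**Little depends on the intervals.** Section 6.2 disclaims efficacy conclusions, Section 11.1 makes description the main focus, and the criteria in Section 8 use recruitment, retention and attendance. This stands and sets the severity.

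**The sample may exceed 60.** A participant with either follow-up enters the model. This is true, but even at 75 the interval is still about 3.5% too narrow.

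**Conclusion.** The point holds and is minor. The SAP leaves the estimator and the degrees-of-freedom method unspecified in a small trial. On the code as it can be read, with only the separators restored, the analysis is ML with normal-based intervals. At 60 participants the variance is then about 5% low, the 95% intervals are about 4 to 5% too narrow, and coverage is about 94%. The corresponding tests would have a type I error of about 6% in place of 5%.

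This rests on three assumptions: no option was lost from the damaged line; the software default is as described; and the follow-up correlation lies in the range tried, which hardly changes the result. It does not show that any feasibility decision, or the size of the definitive trial, would be wrong.

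**What to change.** - In Section 11.4, state that the models are fitted by REML with a named small-sample degrees-of-freedom method, for example Kenward-Roger.
- In Table 16.2, add `reml dfmethod(kroger)` to the `mixed` call. If the source file already has such options, restore the line in full.
- Obtain both treatment contrasts with `lincom ..., small` in place of `lincomest`, so that the intervals and p-values use those degrees of freedom.
- State that any SD carried to the definitive trial comes from the REML fit or from the descriptive SDs in Table 13.4.

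The cost is two options, one changed command and two sentences. Intervals become roughly 4 to 5% wider at 60 participants (1/0.960 = 1.042 to 1/0.954 = 1.048). That range comes from REML with t on 57 degrees of freedom; Kenward-Roger itself was not run and may differ slightly.
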